4.4.2.2 Overall Survival

OS is defined as the time from randomization until the date of death from any cause. For patients still alive at the time of analysis, the data will be censored at the date the patient was last known to be alive. If no post-randomization disease assessment is available, the data will be censored on the randomization date. The duration of OS will be calculated as the date of death or censoring date minus the randomization date plus 1 day, converted to months.

The study is not powered for OS, so adequate power statistical testing for this endpoint is not possible. However, some standard OS estimates will be provided by using the same analysis methods as those described for the primary endpoint of DFS.

The final OS analysis for Cohorts 1 and 2 will be performed after the occurrence of approximately 107 and 118 deaths, respectively (projected to occur at approximately Month 72 in each cohort) or at Month 72, whichever occurs first. One interim analysis of OS is planned in each of the two cohorts at the time of the final DFS analysis for both cohorts (see Section 4.9).

OS will be compared between the two treatment arms using a two-sided stratified log-rank test at an overall two-sided 0.05 significance level for Cohort 1 and Cohort 2 separately. The HR for death will be estimated using a stratified Cox model. Two-sided 95% CIs for the HR will be provided.

Stratified analyses will incorporate the same stratification factors for the analysis of DFS.

Kaplan-Meier methodology will be used to estimate median OS and landmark (e.g., 1-year, 2-year, and 3-year) OS rates and the associated two-sided 95% CIs for each treatment arm, and the Kaplan-Meier curves will be provided.

As a sensitivity analysis, an unstratified log-rank test will be performed and the unstratified HR will be provided.

As an exploratory analysis, OS analyses on the basis of the pooled data from both cohorts will also be performed for descriptive purposes to characterize the benefit of vemurafenib in the total study population.

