4.5.2.7 Survival and New Primary Malignancy Follow-Up Assessments

Survival follow-up information will be collected via telephone calls and/or clinic visits every 13 ± 2 weeks until death, loss to follow-up, or study termination by Roche or *until end of study (see Section 3.2)*. Patients will be followed for new primary malignancies *until end of study (see Section 3.2)*. All patients will be followed for survival information and new primary malignancy unless the patient requests to be withdrawn from follow-up; this request must be documented in the patient's medical record and signed by the investigator. If the patient withdraws from study follow-up, the study staff may use a public information source (such as county records) to obtain information about survival status only.

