4.6.1.2 Withdrawal from Study

The primary reason for withdrawal from the study should be documented on the appropriate eCRF. If patient is lost to follow-up, the investigator should make every effort to contact the patient by telephone or by sending a registered letter to establish as completely as possible the reason for the withdrawal and survival status. These steps for contacting patients (who prematurely withdraw or who are lost to follow-up) will be documented in the patient informed consent form.

Patients who withdraw their consent to be followed for the primary study endpoint (DFS) will be asked to continue follow-up for OS until *end of study* (see Section 3.2), as well as for new primary malignancies until *end of study* (see Section 3.2). Patients will not be followed for any reason after full consent, for DFS, OS, and new primary malignancies, has been withdrawn. Patients who withdraw from the study will not be replaced.

An excessive rate of withdrawals can potentially render the study non-interpretable; therefore, unnecessary withdrawal of patients should be avoided. Should a patient decide to withdraw, all efforts will be made to complete and report the observations prior to withdrawal as thoroughly as possible.

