6.4.2.2 Overall Survival

OS is defined as the time from randomization until the date of death from any cause. For patients still alive at the time of analysis, the data will be censored at the date the patient was last known to be alive. The study is not powered for OS, so adequate power statistical testing for this endpoint is not possible. However, some standard OS estimates will be provided by using the same analysis methods as those described for the primary endpoint of DFS.

Two OS analyses are planned for each cohort. The OS interim analysis in each cohort will be performed at the time of the final DFS analysis for both cohorts. The final OS analysis for Cohorts 1 and 2 will be performed *at the end of study* (see Section 3.2).

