3.2	Independent Review Facility	10
3.3	Data Monitoring	10
4.	STATISTICAL METHODS	10
4.1	Analysis Populations	10
4.1.1	Intent-to-Treat Population.....	10
4.1.2	Safety Population	10
4.1.3	Pharmacokinetic-Evaluable Population	10
4.2	Analysis of Study Conduct.....	10
4.3	Analysis of Treatment Group Comparability	11
4.4	Efficacy Analysis.....	11
4.4.1	Primary Efficacy Endpoint.....	11
4.4.2	Secondary Efficacy Endpoints.....	13
4.4.2.1	Distant Metastasis-Free Survival	13
4.4.2.2	Overall Survival	13
4.4.2.3	Patient-Reported Outcomes	14

4.4.2.4	Type I Error Control for the Secondary Efficacy Endpoints.....	14
4.4.3	Subgroup Analyses	15
4.5	Pharmacokinetic and Pharmacodynamic Analyses	16
4.5.1	Pharmacokinetic Analyses.....	16
4.6	Exploratory Analyses	16
4.7	Safety Analyses	16
4.7.1	Exposure of Study Medication	16
4.7.2	Adverse Events	17
4.7.3	Deaths	17
4.7.4	Laboratory Data	18
4.7.5	Vital Signs.....	18
4.8	Missing Data	18
4.9	Interim Analyses	18
4.9.1	Efficacy	18
5.	REFERENCES	20

LIST OF TABLES

Table 1	Assumptions and Characteristics for Disease-Free Survival Analyses by Cohort.....	9
Table 2	Assumptions and Characteristics for Overall Survival Analyses by Cohort.....	19

LIST OF APPENDICES

Appendix 1	European Organisation for Research and Treatment of Cancer 30-Item Quality of Life Questionnaire (Version 3).....	21
------------	---	----

1. **BACKGROUND**

The Study GO27826 was designed as a pivotal study to support the submission of a supplemental New Drug Application for the use of vemurafenib for the adjuvant treatment of patients with surgically resected, cutaneous malignant melanoma at high risk for recurrence. This Statistical Analysis Plan (SAP) provides the planned analyses for Study GO27826. For purposes of registration, the analyses outlined in this SAP will supersede those specified in the protocol.

2. **STUDY DESIGN**

Study GO27826 is a Phase III, international, multicenter, double-blind, randomized, placebo-controlled study in patients with completely resected, *BRAF*^{V600} mutation-positive melanoma, as detected by the **cobas**[®] BRAF V600 Mutation Test, at high risk for recurrence.

Approximately 475 patients will be enrolled into two separate cohorts:

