4.4.2 Secondary Efficacy Endpoints

4.4.2.1 Distant Metastasis–Free Survival

DMFS is defined as the time from randomization until the date of diagnosis of distant (i.e., non-locoregional) metastasis or death from any cause. For patients without a DMFS event at the time of data cutoff, the data will be censored at the date of the last disease assessment. If no post-randomization disease assessment is available, the observation will be censored on the randomization date.

DMFS will be analyzed at the time of the final DFS analysis in each cohort. The analysis methods to be employed for DMFS are the same as those described for the primary endpoint of DFS.

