4.8 MISSING DATA

For DFS, data from patients who are lost to follow-up without DFS event will be censored at the date of the last disease assessment. If no post-randomization disease assessment is available, the data will be censored on the randomization date.

For DMFS, data from patients who are lost to follow-up without documented distant melanoma recurrence will be censored at the date of the last disease assessment. The data of the patients without post-randomization disease assessments will be censored on date of randomization.

For OS, data from patients who are lost to follow-up will be analyzed as censored observations on the date the patient was last known to be alive. The data of patients without post-randomization disease assessments will be censored on date of randomization.

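### The SAP's fallback for OS censors at randomization when there is no disease assessment, contradicting its own last-known-alive rule; the effect is probably very small

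*SAP*

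**What the plan says.** SAP 4.4.2.2 gives two OS censoring rules in succession. The first censors patients still alive at the date last known alive, in the same terms as Protocol 6.4.2.2: "the data will be censored at the date the patient was last known to be alive". The second is "If no post-randomization disease assessment is available, the data will be censored on the randomization date". OS duration is then the death or censoring date minus the randomization date plus 1 day.

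The OS paragraph of SAP 4.8 starts with patients lost to follow-up, again using the date last known alive, and then says "The data of patients without post-randomization disease assessments will be censored on date of randomization". That sentence is not restricted to living patients.

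The DMFS rule in SAP 4.4.2.1 is almost identical: "If no post-randomization disease assessment is available, the observation will be censored on the randomization date". SAP 4.4.1 has an equivalent rule for DFS. Protocol 6.4.2.2 has no disease-assessment condition for OS.

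The protocol collects survival status by its own route. Section 4.5.2.7 says "All patients will be followed for survival information and new primary malignancy unless the patient requests to be withdrawn from follow-up", with telephone or clinic contacts every 13 ± 2 weeks. Section 4.6.1.2 says that patients who withdraw consent for DFS follow-up "will be asked to continue follow-up for OS". Appendix 1 (footnote mm) adds a final survival contact for all patients at end of study. The limit is complete withdrawal of consent, where Section 4.6.1.2 begins "Patients will not be followed for any reason after full consent".

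On precedence, SAP 1 says that, for registration purposes, "the analyses outlined in this SAP will supersede those specified in the protocol".

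**The concern.** DFS and DMFS cannot be observed without a disease assessment, so a patient with none has no follow-up for those endpoints, and censoring at randomization is correct. OS needs only to know whether the patient is alive, and on what date. For someone known to be alive from a telephone call but never assessed for disease, the two sentences in SAP 4.4.2.2 give different censoring dates. The second replaces known survival time with 1 day.

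If survivors in this group are removed on day 1 while deaths in it still count, censoring depends on outcome and OS estimates are pulled down. If the SAP 4.8 sentence is applied literally, a known death could also be censored at randomization. In both cases randomized patients with usable survival data contribute almost nothing to an analysis meant to include everyone randomized.

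**Working it through.** **Who could be affected.** Protocol 3.1 counts physical examination as part of recurrence surveillance and starts dosing within 4 calendar days of randomization. Section 4.5.2.1 requires an examination at Cycle 1, Day 1 unless one was done within 7 days. Section 4.5.2.2 requires another at Day 15. A dosed patient will therefore usually have an assessment within weeks. What remains is mainly patients never dosed, or lost at once, who are still under survival contact. The group would be larger if only scans counted (first due at 13 ± 2 weeks). The SAP does not define the term.

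**The plan's own OS figures.** SAP Table 2 gives power of 0.45 and 0.49 for HR 0.70 with 107 and 118 deaths. With power = Φ(|ln HR| × √(d/4) − 1.96):

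- d = 107: 0.3567 × 5.172 = 1.845, and Φ(−0.115) = 0.454.
- d = 118: 0.3567 × 5.431 = 1.937, and Φ(−0.023) = 0.491.

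Both reproduce. They depend on the number of deaths, so moving the censoring date of living patients does not change them.

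**Illustrative size.** The documents give no number of affected patients. Assume k = 1 or 2 living patients per arm in each cohort: 4 to 8 of 475, or 0.8% to 1.7%. Other inputs are the control medians of 61 and 24.2 months (SAP Table 2), 1:1 allocation of 300 and 175 patients (n = 150 and 87.5 per arm), exponential survival, affected patients alive beyond 2 years, and deaths kept as events.

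With f = k/n and S = exp(−ln 2 × 24/median), removing k survivors on day 1 changes the 2-year rate to (S − f)/(1 − f).

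| Control arm | S | k = 1 | k = 2 | Fall in points |
|---|---|---|---|---|
| Cohort 1 | 76.13% | 75.97% | 75.81% | 0.16 to 0.32 |
| Cohort 2 | 50.29% | 49.71% | 49.12% | 0.57 to 1.16 |

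Falls are from unrounded values.

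The Cohort 2 control median solves S = 0.5(1 − f) + f. This gives 23.80 months (k = 1) and 23.41 months (k = 2), against 24.2.

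The 95% half-width of the 2-year rate, ignoring censoring, is 1.96 × √(S(1 − S)/n): 6.8 points in Cohort 1 and 10.5 in Cohort 2. Every shift above is much smaller.

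**Follow-up lost.** If each affected patient is known alive at about 30 months (the Protocol Table 5 cutoff after the last patient in), 4 × 2.5 = 10 to 8 × 2.5 = 20 patient-years become days. Protocol 3.2 times minimum follow-up from Cycle 1, Day 1, which a never-dosed patient lacks, so the 2.5 years is also an assumption.

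**Treatment comparison.** With equal numbers in both arms and 30 months of follow-up, the crude rate ratio, using d/(PT − 30k) in each arm (d deaths, PT person-months), is 0.7003, 0.7001 and 0.6998 in Cohort 1 and 0.6994, 0.6981 and 0.6968 in Cohort 2 for k = 0, 1 and 2. It stays at 0.70.

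**Literal reading of SAP 4.8.** The whole group, dead or alive, would leave on day 1. The selective loss of survivors disappears, but deaths are lost. If 1% of deaths were dropped, power would be 0.4505 and 0.4871, still 0.45 and 0.49 when rounded.

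**The case against.** The strongest reply is that the fallback is ordinary shorthand for patients with no follow-up at all, and that a programmer would use the last-known-alive date wherever one exists. That may be the intention, but the condition as written is absence of a disease assessment, and it appears in two sections.

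A second reply is that Protocol 6.4.2.2 may govern. This has force. A reader might infer from SAP 1 that the SAP rule necessarily controls the OS analysis. The documents do not support that: the precedence is limited to registration, and the rationale for Protocol Version 10 says registration is no longer pursued. That version also post-dates SAP Version 4 and moves the final OS analysis to end of study. Which text governs the final OS analysis is arguable. The conflict inside SAP 4.4.2.2 remains in either case.

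Third, the number affected could be zero, and the direction of bias depends on keeping deaths as events. SAP 4.4.2.2 implies this, since its fallback follows a sentence about living patients; SAP 4.8 does not say so. Both points stand, and the figures above are illustrations only.

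Fourth, nothing inferential turns on it. OS is not powered. Because DFS was not significant in Cohort 2, the hierarchy in SAP 4.4.1 and 4.4.2.4 leaves OS without a formal test in either cohort. That is correct, but OS medians, landmark rates and hazard ratios are still to be reported.

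**Conclusion.** The OS fallback is wrong as written. It makes OS censoring depend on an assessment that OS does not need, conflicts with the preceding sentence in SAP 4.4.2.2, and can discard survival status that the protocol collects. This follows from the text and needs no assumption about numbers.

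The consequence is minor. Under the stated assumptions, 2-year control-arm OS moves by at most about 0.3 points in Cohort 1 and 1.2 points in Cohort 2. Downward bias is the expected direction only if deaths in the affected group are kept.

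A reader might go further and infer a biased hazard ratio. Assumed shares of 2% on placebo and 8% on vemurafenib would give an apparent hazard ratio of about 1.03 to 1.05 when there is no effect, but nothing in the documents suggests shares that large or that unequal. Nor do they show that any known death has been dropped; SAP 4.8 only leaves that possible.

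**What to change.** In SAP 4.4.2.2 and the OS paragraph of SAP 4.8, replace the fallback and merge it with the existing last-known-alive sentence so that the rule is stated once in each place:

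> Deaths on or before the data cutoff are counted as events regardless of disease assessments. Patients not known to have died by the cutoff are censored at the last date known alive from any source permitted by their consent; only patients with no post-randomization survival information are censored on the randomization date.

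The DFS and DMFS rules stay as they are. No new data are needed, and planned events and power are unchanged. The primary analysis has already been done, with the OS interim scheduled alongside it, so the change should be documented as a correction made after those results, with the number of affected patients by arm and cohort. If that number is zero, no estimate changes. The OS section of the SAP needs revisiting anyway, because its final-analysis timing (107 and 118 deaths, or Month 72) differs from the end-of-study timing in the current protocol.

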4.4.2.3 Patient-Reported Outcomes

Quality of life (QoL), as measured by EORTC QLQ-C30, will be evaluated for patients with a baseline assessment and at least one post-baseline QLQ-C30 assessment that generate a score. Total QLQ-C30, each domain score (i.e., physical functioning, role functioning, emotional functioning, cognitive functioning, and social functioning), symptom scales, and their changes from baseline will be examined for each timepoint with use of descriptive statistics, including mean, median, standard deviation, and range.

Compliance rates for patients who complete PRO assessments will be assessed over time and by treatment arm.

See [Appendix 1](#) for a description of the calculation of each domain score and the total QLQ-C30.

4.4.2.4 Type I Error Control for the Secondary Efficacy Endpoints

The following procedure will be performed separately for each cohort, provided that the cohort is statistically significant in the primary DFS analysis (according to the rules described in Section 4.4.1).

To control the Type I error rate at the 0.05 level (two sided) for the secondary efficacy endpoint tests, a hierarchical testing approach will be employed to evaluate the statistical significance of the secondary endpoints of DMFS and OS. If the primary DFS analysis meets statistical significance in either cohort, DMFS and then OS will be evaluated for statistical significance at the 0.05 level (two sided) for that cohort.

The secondary endpoint of DMFS will be compared between treatment arms using a two-sided stratified log-rank test at an overall two-sided 0.05 significance level for Cohorts 1 and 2 separately. For each cohort, if the DFS comparison is positive in favor of vemurafenib, the comparison of DMFS between the placebo and vemurafenib arms will be tested at an overall two-sided 0.05 significance level for each cohort. Gated on the successful testing of the comparison of the secondary endpoint, DMFS, in each cohort, the secondary endpoint of OS will be compared between treatment arms using a two-sided stratified log-rank test at an overall two-sided 0.05 significance level for Cohorts 1 and 2 separately. The Lan-DeMets implementation ([Lan and DeMets 1983](#)) of the O'Brien-Fleming use function will be used to control the overall Type I error for the OS comparison in each cohort at a two-sided 0.05 significance level. See Section [4.9.1](#) for details.

4.4.3 Subgroup Analyses

The consistency of the treatment effect of vemurafenib on DFS, OS, and DMFS across subgroups defined by demographic and baseline characteristics and stratification factors will be examined within each cohort. Because some subgroups may have small sample sizes, these analyses will be considered exploratory.

The subgroups to be considered include, but are not limited to, the following:

- Disease stage (Stage IIC, Stage IIIA, and Stage IIIB) for Cohort 1
- Age (≤ 50 years, > 50 years) at randomization
- Age (≤ 65 years, > 65 years) at randomization
- Tumor ulceration (or mitosis $\geq 1/\text{mm}^2$ for T1 lesions) present or not present at randomization
- Race (non-White, White)
- Sex (female, male)
- Region (North America, Australia/New Zealand/South Africa/Latin America, rest of the world)
- Eastern Cooperative Oncology Group Performance Status at randomization (0 or 1)
- Newly diagnosed versus first metachronous recurrence
- Lymph node types: macroscopic, microscopic, and N3 at randomization

- *BRAF* mutation status such as V600E versus non-V600E at randomization

For DFS, OS, and DMFS, the Kaplan-Meier estimated median time will be summarized by treatment arm for each of the subgroups defined above along with a HR (treatment:control) estimated by unstratified Cox regression that is displayed as a Forest plot (Lewis and Clarke 2001).

4.5 PHARMACOKINETIC AND PHARMACODYNAMIC ANALYSES

4.5.1 Pharmacokinetic Analyses

Descriptive statistics will be used to perform the analysis of plasma concentrations of vemurafenib at clinically relevant timepoints. These timepoints will include all available Cycle 1 data and pre-dose values from all available cycles. In addition, summary statistics may be provided for PK data from patients following the diagnosis of melanoma recurrence or occurrence of a new primary melanoma during study treatment, at the time of diagnosis of SCC (cutaneous [including KA] and non-cutaneous), and at the occurrence of dose-limiting toxicity and concomitant decision to reduce the dose or interrupt or discontinue treatment. The descriptive statistics will include arithmetic means, standard deviations, geometric means, coefficients of variation, medians, and ranges.

Plasma concentrations that are below the limit of quantification for the assay will be replaced with zero for descriptive statistics. Missing PK data points will not be replaced. Pre-dose values that are determined to be measured post-dose will not be included in the analysis.

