For select patients described in Section 4.5.1.7, colonoscopy to the cecum, with adequate bowel preparation, by a gastroenterologist or his or her designee (unless colonoscopy to the cecum with adequate bowel preparation and adequate resection of all visualized polyps was performed within 1 year of the start of the 90-day screening period)

Note: All polyps found at the screening colonoscopy will need to be adequately resected.

Please note that a patient with a known personal history of more than three (>3) adenomatous colorectal polyps or a personal history of adenomatous colorectal polyp(s) >2 cm in size will be excluded from this study; this also applies to the screening colonoscopy for select patients (see Section 4.1.2).

Concomitant medications

- Within 28 days prior to randomization:
 - Medical history, complete physical examination (including height and weight), and vital signs
 - Thorough head and neck examination by the investigator
 - Hematology, coagulation screening studies, serum chemistry, and liver function tests
 - Hepatitis B virus (HBsAg and total anti-HBc) and HCV serology
 - Triplicate ECGs
- Within 14 days prior to randomization:
 - Serum pregnancy test

The following assessments are required on Cycle 1, Day 1 (prior to administration of study drug):

- Baseline PRO assessment (i.e., EORTC QLQ-C30 questionnaire)
- Triplicate ECG
 - Note: If the screening ECG was performed within 7 days of the Cycle 1, Day 1 visit, it does not have to be repeated at Day 1.
- Vital signs, physical examination
 - Note: If vital signs and physical examination are assessed within 7 days of the Cycle 1, Day 1 visit, they do not have to be repeated at Day 1.

- Hematology, serum chemistry, and liver function tests
 - Note: If screening laboratory specimens are collected within 7 days of the Cycle 1, Day 1 visit, they do not have to be repeated at Day 1.
- Blood samples for PK assessments (pre-dose, 1–4 hours after dose)
- Serum and plasma samples for exploratory biomarker assessments (6 mL in EDTA; 6 mL in serum separator tube)
- An optional whole blood sample (6 mL in EDTA) will be collected from patients consenting to provide a sample for the RCR.
 - Note: This specimen can be collected at the first visit following the RCR consent if this occurs after Cycle 1, Day 1.

See [Appendix 1](#) for the schedule of screening and pretreatment assessments.

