6.6 PHARMACOKINETIC ANALYSES

The PK-evaluable population will include all patients who have received at least one dose of vemurafenib and have provided valid PK assessments. Summary statistics will be used as appropriate to perform the descriptive analysis of the plasma concentrations of vemurafenib at clinically relevant timepoints. These timepoints will include all available Cycle 1 data and predose values from all available cycles. In addition, summary statistics may be provided for PK data from patients after the diagnosis of melanoma recurrence or occurrence of a new primary melanoma during study treatment, at the time of diagnosis of SCC (cutaneous [including KA] and non-cutaneous), and at the occurrence of a dose-limiting toxicity and concomitant decision to reduce the dose or interrupt or discontinue treatment. All PK parameters will be presented descriptively including arithmetic means, standard deviations, geometric means, coefficients of variation, medians, and ranges.

In the scenario, in which major discrepancies are observed in the exposure levels and in the PK characteristics, nonlinear mixed-effects modeling (with software NONMEM [Beal and Sheiner 1998]) will be used to analyze the sparse PK concentration–time data for vemurafenib, and the results of these analyses will be reported in a document separate from the Clinical Study Report.

Graphical analyses will be conducted to explore the possible relationship between vemurafenib exposure and the following parameters:

- The risk of melanoma recurrence or the occurrence of a new primary melanoma
- The occurrence of serious adverse events
- The abnormalities in selected safety laboratory parameters

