4.1.3 Pharmacokinetic-Evaluable Population

The PK-evaluable population will include all patients who have received at least one dose of vemurafenib and have provided valid PK assessments. The PK-evaluable population will be analyzed according to the treatment received. The PK population at specific timepoints will vary, depending on the availability of results at confirmed dosing and PK assessment times.

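### SAP 4.5.1 sets concentrations below quantification to zero but also reports geometric means, which become 0 or undefined wherever one such value occurs

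*SAP*

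**What the plan says.** SAP 4.5.1 specifies the PK summaries: "The descriptive statistics will include arithmetic means, standard deviations, geometric means, coefficients of variation, medians, and ranges". On timing it says: "These timepoints will include all available Cycle 1 data and pre-dose values from all available cycles". Its next paragraph gives the data-handling rules: "Plasma concentrations that are below the limit of quantification for the assay will be replaced with zero for descriptive statistics", and then "Missing PK data points will not be replaced". A further rule removes pre-dose values found to have been drawn after dosing. Nothing in the section treats the geometric mean differently from the other statistics.

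Protocol 6.6 promises the same list: "All PK parameters will be presented descriptively including arithmetic means, standard deviations, geometric means, coefficients of variation, medians, and ranges". It has no rule for values below quantification.

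Protocol 4.5.2.1 and Appendix 2 schedule a sample before the first dose on Cycle 1 Day 1. Protocol 4.5.2.2 adds unscheduled samples, for example immediately before treatment resumes after a drug holiday and at the visit closest after discontinuation.

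**The concern.** Two instructions in one SAP section cannot both be followed to a sensible result. A geometric mean is defined for positive values, and the substitution rule puts zeros into it. Followed literally, one below-quantification sample turns the geometric mean for that timepoint into 0. Alternatively, whoever produces the table leaves the zeros out, and the geometric mean then rests on fewer patients than the arithmetic mean beside it, under a rule written nowhere.

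What is at stake is the PK table. Describing vemurafenib pharmacokinetics is a secondary objective (Protocol 2.2), and steady-state trough concentrations are among the named PK outcome measures (SAP 2.1.4). SAP 4.5.1 specifies descriptive statistics as its PK analysis.

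**Working it through.** The plan states no figure to reproduce, so the check is on the definition, and then on how often the problem could arise.

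**1. Definition.** GM = (x₁ × … × xₙ)^(1/n) = exp(mean of ln xᵢ). If any xᵢ = 0, the product is 0 and GM = 0 for every n. In the log form ln 0 does not exist, so GM is undefined, as is the standard deviation of the logs.

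**2. Numerical illustration.** Log-normal concentrations were simulated with median 59 µg/mL (the steady-state minimum concentration in Protocol 1.2.3), an assumed CV of 40% and n = 100. One value was then set to zero.

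| Statistic | All quantifiable | One value set to 0 |
|---|---|---|
| Geometric mean (µg/mL) | 57.44 | 0 |
| Arithmetic mean (µg/mL) | 60.79 | 60.20 |
| Median (µg/mL) | – | 59.14 |
| Arithmetic CV | – | 0.357 |

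The geometric mean is also 0 at n = 20 (59.86 without the zero) and n = 230 (55.98 without it). Only the geometric mean fails.

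**3. Where it is expected.** All Cycle 1 data are summarised, and these include the sample before the first dose. Those values should all be below quantification.

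**4. How long off drug before a trough is unquantifiable.** Protocol 1.2.3 gives a median accumulation ratio R of 7.36 for twice-daily dosing. Assuming simple first-order accumulation with a 12-hour interval:

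- R = 1 / (1 − e^(−12k)), so e^(−12k) = 1 − 1/7.36 = 0.864 and k = 0.0122 per hour.
- Effective half-life = ln 2 / k ≈ 57 hours.
- From 59 µg/mL to 1 µg/mL: ln(59)/k ≈ 335 hours, about 14 days.
- From 59 µg/mL to 0.01 µg/mL: ln(5900)/k ≈ 714 hours, about 30 days.
- From 5.4 µg/mL, the lowest Day 15 value quoted in Protocol 1.2.3: about 6 days to 1 µg/mL and 22 days to 0.01 µg/mL.

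The limits of 1 and 0.01 µg/mL are assumptions. Protocol 4.3.2.1 ends study treatment after a break of more than 28 consecutive days. A sample taken just before resumption can therefore follow up to 28 days off drug, when a typical patient would be at about 0.017 µg/mL.

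**5. Chance that a timepoint is affected.** If a share p of values is below quantification, the chance of at least one among 100 is 1 − (1 − p)^100. For assumed p of 0.5%, 1%, 2% and 5% this is 39%, 63%, 87% and 99%. The documents give no p.

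**6. Candidate repairs.** In the n = 100 example, leaving the value out gives 57.42. Replacing it with half the lower limit of quantification (LLOQ/2) gives 52.30, 53.52, 54.38 and 54.76 for an assumed LLOQ of 0.01, 0.1, 0.5 and 1 µg/mL. If 5% of values were replaced around a geometric mean of 59, the multiplier would be (0.5/59)^0.05 = 0.79 for an LLOQ of 1, and (0.005/59)^0.05 = 0.63 for an LLOQ of 0.01. Those are reductions of 21% and 37%.

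**The case against.** The best defence is that the flaw does little harm. At Cycle 1 Day 1 pre-dose a geometric mean of 0 or not calculable misleads nobody. At a later trough, a geometric mean of 0 beside a median near 59 µg/mL would be seen at once as an artefact. The usable statistics are printed alongside, SAP Section 4 already asks for the number of patients with continuous summaries, and the zero rule is confined to descriptive statistics, so it does not govern the population PK modelling in Protocol 6.6. All of this stands, and it is why the point is minor. The modelling is less of a safeguard than it seems, since Protocol 6.6 makes it conditional on major discrepancies in exposure or PK characteristics.

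A second defence is that SAP 4.1.3 lets the PK population vary by timepoint with the availability of results at confirmed dosing and assessment times. That covers missing or mistimed samples. A below-quantification result is an available result, and 4.5.1 says to set it to zero.

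A third is that a programmer would deal with the zeros sensibly. Neither document names software or a table layout, so what would happen is unknown. Any such handling would replace the written rule with an unwritten one.

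**Conclusion.** The inconsistency is real, and nothing in either document resolves it. At any timepoint with at least one value below quantification, the stated rules give a geometric mean of 0 or none at all. That follows from the definition and needs no assumption. How often it would occur after the first dose cannot be determined without the LLOQ and a below-quantification rate.

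Three stronger readings are tempting but unsupported:

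- **The summary is wrong wherever a patient was off drug.** With an effective half-life of about 57 hours, short interruptions would usually leave quantifiable drug. The half-life assumes first-order accumulation, and Protocol 1.2.3 reports high between-patient variability, so individual patients may differ.
- **About half of patients would be affected.** Protocol 5.1.1 says about half of earlier patients needed an interruption and/or reduction at least once. It gives no durations, a dose reduction does not by itself imply an unquantifiable value, and the figure is not a below-quantification rate.
- **The variability measure also fails.** The SAP lists coefficients of variation without calling them geometric, and an arithmetic CV remains computable.

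The DFS, DMFS, OS and safety analyses are untouched.

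**What to change.** Amend the rule in SAP 4.5.1 as follows:

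- Keep zero for arithmetic means, standard deviations, medians and ranges.
- Calculate geometric means on quantifiable values only.
- Do not report a geometric mean for Cycle 1 Day 1 pre-dose.
- Print n and the number of below-quantification values at every timepoint.
- Use LLOQ/2 at most as a sensitivity check, once the LLOQ is stated. It should not be the main rule, because its result depends on that limit.

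The cost is a sentence or two in the SAP and one extra count in the PK tables. The drawback is that the geometric mean then describes quantifiable samples only and is slightly high when values have been excluded. The printed count makes this visible.
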